7. PRIMARY STATISTICAL ANALYSES

7.1. Primary Efficacy Analyses

7.1.1. Overview of Planned Primary Efficacy Analyses

The primary efficacy parameter after the 2nd year of the study is change from baseline IPSS (International Prostate Symptom Score). The IPSS questionnaire consists of seven questions with each question score ranging from 0 to 5. It is administered at screening, baseline, and at each of the scheduled post-baseline treatment phase visits.

IPSS (also called IPSS total score) is the sum of the seven questions. IPSS summaries and analyses will be in terms of the total (score); exceptions will be noted such as for supporting summaries of individual questions. For calculation of the IPSS total, missing individual responses will be imputed when at least four of the seven questions are answered (nonmissing). For the imputation, the average of the nonmissing responses will be calculated and rounded to the nearest integer. This average will be imputed for the original missing response(s). If at least 20% of the subjects have at least one imputed IPSS then the statistical analyses will be repeated based on non-imputed scores.

The efficacy analyses will be based on the Intent-to-Treat (ITT) population. [Table 3](#) provides an overview of the planned IPSS summaries and primary efficacy analyses. A list of planned data displays is in [Appendix 15](#): List of Data Displays.

Table 3 Overview of Planned Primary Efficacy Analyses

Endpoint	Absolute			Change from Baseline			% Change from Baseline		
	L	F	T	L	F	T	L	F	T
IPSS (International Prostate Symptom Score) Change from Baseline									
Primary Analysis (Month 24 Visit)	Y ^[1]			Y	Y ^[1]	Y	Y ^[2]		
Supporting and Sensitivity Analyses of Primary Endpoint									
Mixed-Model Repeated-Measures (MMRM) Analysis (At Visit)						Y			
IPSS Change from Baseline by Subgroup ^[3]						Y			
Individual IPSS Questions	Y ^[1]		Y			Y			
IPSS Percentage Change from Baseline							Y ^[1]		Y
IPSS Non-imputed Score Analysis ^[4]			Y		Y	Y			
IPSS Per-Protocol Population Analysis ^[5]			Y		Y	Y			

NOTES :

- T = Table, F = Figure, L = Listing, Y = Yes display generated. All outputs are based on ITT population except [4].
- Tables and figures have separate outputs for LOCF and At Visit, except for baseline summaries.
- 1. Individual questions 1 – 7 responses, total score, total score change from baseline, and percentage change from baseline are combined in a single listing and presented for every visit.

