7.1.2. Planned Primary Efficacy Statistical Analyses

Endpoint: The primary efficacy parameter is the change from baseline IPSS at Year 2 (Month 24) using the last observation carried forward approach (LOCF) based on the Intent-to-Treat (ITT) population.

[Table 3](#) provides an overview of the planned IPSS summaries and primary efficacy analyses. A list of planned data displays is in [Appendix 15](#): List of Data Displays.

Baseline and change from baseline are defined in [Appendix 6](#). Last observation carried forward (LOCF) and At Visit approaches are defined in [Appendix 7](#).

Note: IPSS timepoints earlier than Month 24, specifically Month 21 – Month 3, in this order, are classified as secondary endpoints. Summaries and analyses of these timepoints will be conducted in same manner and on same outputs as the primary analyses.

Reference [Table 4](#).

Model Specification and Results Presentation: Change from baseline IPSS at each scheduled post-baseline assessment will be compared in terms of combination treatment versus tamsulosin treatment using t-tests from a general linear model (GLM) with effects for treatment, cluster, and baseline IPSS. Two-sided tests at 0.05 level of significance will be conducted.

The adjusted mean estimates (mean and standard error), the adjusted mean difference, and the 95% confidence interval in terms of the adjusted mean difference will be presented. The adjusted mean difference will be in terms of combination treatment minus tamsulosin treatment. The model results will be presented on same tabular summary as the arithmetic mean, standard deviation, median, minimum and maximum. The results will be presented by treatment for each scheduled post-baseline assessment.

IPSS adjusted mean change from baseline will be plotted by treatment for each post-baseline scheduled visit in terms of each LOCF and At Visit approach.

Multiple Comparisons and Multiplicity: Reference [Appendix 11](#), Multiple Comparisons and Multiplicity.

Model Checking and Diagnostics: Reference [Appendix 12](#), Model Checking and Diagnostics for Statistical Analyses.

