8.1.4. Maximum Urine Flow (Qmax)

Qmax and associated total voided volume are measured at screening (Visit 1a with possible repeat at Visit 1b), baseline, and at each Month 6, Month 12, Month 18, and Month 24 (or end of treatment) visits. Qmax change from baseline is a secondary efficacy endpoint. Qmax measurements with voided volumes <125 ml will not be included in the analysis.

[Table 4](#) provides an overview of the planned Qmax summaries and analyses. A list of planned data displays is in [Appendix 15](#): List of Data Displays. Baseline, change from baseline, and percentage change from baseline are defined in [Appendix 6](#). Last observation carried forward (LOCF) and At Visit approaches are defined in [Appendix 7](#). Summaries and analyses will be in terms of the ITT population; LOCF approach will be considered primary. Qmax summary statistics will be presented for each scheduled visit; change from baseline and percentage change from baseline will be presented for each scheduled post-baseline visit.

Change from baseline Qmax at each scheduled post-baseline assessment will be compared in terms of combination treatment versus tamsulosin treatment using t-tests from a general linear model (GLM) with effects for treatment, cluster, and baseline Qmax. Two-sided tests at 0.05 level of significance will be conducted.

The adjusted mean estimates (mean and standard error), the adjusted mean difference, and the 95% confidence interval in terms of the adjusted mean difference will be presented. The adjusted mean difference will be in terms of combination treatment minus tamsulosin treatment. The model results will be presented on same tabular summary as the arithmetic mean, standard deviation, median, minimum and maximum. The results will be presented by treatment for each scheduled post-baseline assessment.

Qmax adjusted mean change from baseline will be plotted by treatment for each post-baseline scheduled visit in terms of each LOCF and At Visit approach.

Qmax improvement is also assessed using categorical changes. Improvement is a post-baseline Qmax which is higher than the baseline Qmax. Worsening is a post-baseline Qmax which is lower than the baseline Qmax. The number and percentage of subjects with Qmax percentage change from baseline categories of 1) improvement, 2) no change, and 3) worsening will be summarized by treatment group using both the LOCF and At Visit approaches at each scheduled post-baseline assessment.

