11.2. Appendix 2: Time & Events

11.2.1. Protocol Defined Time & Events

Study Procedures	Visit 1a Pre-Screen	Visit 1b** Screening (V1a + 14 days)	Visit 2 Baseline (V1b + 28d ± 4 days)	Visit 3 (Baseline + 13 wks ± 14 days)	Visit 4 (Baseline + 26 wks ± 14 days)	Visit 5 (Baseline + 39 wks ± 14 days)	Visit 6 (Baseline + 52 wks ± 14 days)	Visits 7 - 9 (Years 2, repeat as for V3-V5 of Year 1)	Visit 10 (Baseline + 104 wks ± 14 days)
	Pre-Screen Visit	Start of Placebo run-in	Start of Treatment Phase Baseline (Randomization)	3 months post Randomization (Rand)	6 months post Rand	9 months post Rand	12 months post Rand	15,18 & 21 months post Rand respectively	End of Treatment Phase 24 months post Rand ⁱ
ICF	X								
Inclusion/Exclusion	X	X							
Medical Hx/ Demog/CV Hx/	X								
ECG (12-lead)		X							
Collection of PGx Sample			X						
Safety evaluations									
Concomitant medication	X	X	X	X	X	X	X	⇒	X
Physical Examination ^a		X			X		X	X ^h	X
Vital signs ^b		X	X	X	X	X	X	⇒	X
Haematology/clinical chemistry	X						X		X
HBsAg and Hepatitis C Antibody ^g			X						
Total serum PSA ^c	X				X		X		X
Post-void residual volume (PVR)	X	X***	X		X		X	X ^h	X
AEs ^d		X	X	X	X	X	X	⇒	X
Suicidality (C-SSRS)	X				X		X		X
Efficacy:									
BPH symptoms (IPSS)	X		X	X	X	X	X	⇒	X
Prostate Volume (TRUS)		X					X		X

Study Procedures	Visit 1a Pre-Screen	Visit 1b** Screening (V1a + 14 days)	Visit 2 Baseline (V1b + 28d ± 4 days)	Visit 3 (Baseline + 13 wks ± 14 days)	Visit 4 (Baseline + 26 wks ± 14 days)	Visit 5 (Baseline + 39 wks ± 14 days)	Visit 6 (Baseline + 52 wks ± 14 days)	Visits 7 - 9 (Years 2, repeat as for V3-V5 of Year 1)	Visit 10 (Baseline + 104 wks ± 14 days)
	Pre-Screen Visit	Start of Placebo run-in	Start of Treatment Phase Baseline (Randomization)	3 months post Randomization (Rand)	6 months post Rand	9 months post Rand	12 months post Rand	15,18 & 21 months post Rand respectively	End of Treatment Phase 24 months post Rand ⁱ
Peak Urine Flow (Qmax)	X	X ^{**}	X		X		X	X ^b	X
AUR or BPH-related Surgery			X	X	X	X	⇒	X	X
Pharmacokinetics^j									
Serum PK samples ^j				X	X	X			
Health Outcomes:									
BPH Health Status Q 8 IPSS (BHS)	X		X	X	X	X	X	⇒	X
AUR or BPH-related Surgery Medical Resource Utilisation			X	X	X	X	X	⇒	X
BPH Impact Index (BII)	X		X	X	X	X	X	⇒	X
PAS-SFI		X	X				X		X
Other Efficacy Measures									
UTI /Incontinence / Renal Insufficiency			X	X	X	X	X	⇒	X
Register in RAMOS	X								
Study Medication:									
Call RAMOS/DispenseMeds		X ^e	X ^f	X	X	X	X	⇒	

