
 A subject's baseline date will be the latest non-missing value of either (double-blind) treatment start date or randomization date. Baseline date will be used in the derivation of study day values and Baseline Values. 'Baseline date' may differ from the Visit 2 (Baseline Visit) date recorded in eCRF.
Baseline Value

 For purposes of data analyses, the subject's baseline value of an assessment will be defined as the latest assessment on or before the Baseline Date.
Change and % Change from Baseline

 Change from Baseline = Post-baseline Value – Baseline % Change from Baseline = $100 \times [(\text{Post-baseline Value} - \text{Baseline}) / \text{Baseline}]$

Study Day																				
Study Day is calculated as the number of days from Baseline Date:																				

 • Reference Date = Missing → Study Day = Missing • Reference Date < Baseline Date → Study Day = Reference Date – Baseline Date • Reference Date ≥ Baseline Date → Study Day = Reference Date – (Baseline Date) + 1 																				
Cut-off Dates																				
-Month k Cut-off Date (for k= 3, 6, 9, 12, 15, 18, 21, 24): The maximum of [Month k clinic visit date, Month k lab visit date, Baseline Date + (k * 91/3)].																				
Time Since LUTS First Noted (in years)																				
-Time Since LUTS First Noted = Baseline Date minus Date LUTS First Noted by Patient / 365																				
Time Since BPH Clinical Diagnosis (in years)																				
-Time Since BPH Diagnosis = Baseline Date minus Date of BPH Clinical Diagnosis / 365																				
Age																				
Only year of birth is collected in the eCRF. For purposes of calculating age for a given subject, date of birth will be defined as June 30 th of the corresponding year of birth. Age is calculated in terms of Screening (Visit 1b) date and output as a truncated integer. Age categories include <65, ≥65, <75, and ≥75 years.																				
Body Mass Index (BMI) (kg/sq m)																				
BMI = Weight (kg) / [Height (m)] ²																				
Race / Ethnicity																				
Race / ethnicity will be determined based on a subject's reported ethnicity and geographic ancestry as defined in the following table.																				

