11.10. Appendix 10: Examination of Covariates and Subgroups

Endpoint(s)	IPSS change from baseline
Analysis	Subgroup Summaries and General Linear Model

A list of subgroups of interest for the primary efficacy endpoint is below. If the categorization defining the subgroups results in overly sparse data or if some baseline subgroups are homogeneous in response, then particular subgroups may be combined or not reported.

For each subgroup, IPSS change from baseline summaries will be output by treatment group at Month 12 and at Month 24 for the ITT population using both LOCF and At Visit approaches. No statistical comparisons will be performed.

The effects of baseline subgroups and their interactions with treatment will be assessed. As a minimum, these subgroups will include those in the below table except for country and center. These effects will be individually explored in terms of: 1) addition of subgroup effect to the model* and 2) addition of subgroup effect and subgroup effect by treatment interaction to the model*.

*Refers to primary efficacy General Linear Model (GLM):

Change from Baseline IPSS = treatment + cluster + baseline IPSS.

In these analyses, continuous variables will be treated as continuous and not as dichotomous subgroups. These assessments will focus on Month 24 LOCF, and separately Month 24 At Visit, and will be output as listings. Other analyses based on other time points will not be output unless substantive finding dictate.

Subgroups Summarized for Primary Efficacy Endpoint	
Subgroup	Categorization for Tabular Summary Display
Baseline Age 65	<65, ≥65 years
Baseline Age 75	<75, ≥75 years
Baseline IPSS	<20, ≥20
Baseline BPH-Related Health Status	<4, ≥4
Baseline Prostate Volume	<40, ≥40cc
Baseline Qmax	<10, ≥10ml/sec
Alpha Blocker History	Yes, No
5-Alpha-Reductase Inhibitor History	Yes, No
Phytotherapy History	Yes, No
Alpha Blocker or 5-Alpha-Reductase Inhibitor History	Yes, No
Alpha Blocker or 5-Alpha-Reductase Inhibitor or Phytotherapy History	Yes, No
Baseline PSA	<3, ≥3ng/ml
Country (cluster)	China, Japan, Korea, Taiwan
Center	Each center with at least one randomized subject.

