11.13. Appendix 13: Mixed-Model Repeated-Measures Analysis

Mixed-Model Repeated-Measures (MMRM) Analysis: As a supportive analysis, IPSS change from baseline will be analyzed using a mixed-model repeated-measures (MMRM) analysis including data from the scheduled post-baseline assessments [Mallinckrodt, 2008]. Analyses will include the fixed, categorical effects of treatment, cluster, visit, and treatment-by-visit interaction, as well as the continuous, fixed covariates of baseline IPSS and baseline IPSS-by-visit interaction. An unstructured covariance structure will be used to model the within-patient errors, shared across treatments. PROC MIXED in SAS [Littell, 1996] will be used to fit the model, using the restricted maximum likelihood estimation method and the Kenward-Roger option to estimate denominator degrees of freedom and standard errors.

Corresponding SAS output will be provided as a listing. The treatment comparison will be the contrast between treatments (Combination minus Tamsulosin) at the Month 24 visit using the two-sided p-value from the corresponding t-test at $\alpha=0.05$. In this supportive analysis, superiority of the Combination vs. Tamsulosin treatment will be declared if the two-sided p-value for the contrast is less than or equal to 0.05 and the observed treatment effect supports superiority. A two-sided 95% confidence interval for the estimated treatment difference in the change from baseline at each scheduled visit will be computed. Estimated mean change from baseline and standard errors will be computed by treatment group and visit. If the model-fitting algorithm fails to converge then alternative initial parameter values and/or covariance structures will be considered.

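### The primary IPSS model and the MMRM adjust for one pre-treatment IPSS although two are collected; adding the Visit 1a score is an optional, modest efficiency gain

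*SAP*

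**What the plan says.** Section 7.1.2 compares the arms at each visit with a "general linear model (GLM) with effects for treatment, cluster, and baseline IPSS". Appendix 10 writes the same model as "Change from Baseline IPSS = treatment + cluster + baseline IPSS". The supportive MMRM in Appendix 13 takes as its baseline terms "the continuous, fixed covariates of baseline IPSS and baseline IPSS-by-visit interaction".

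Appendix 6 fixes which score is meant: the "baseline value of an assessment will be defined as the latest assessment on or before the Baseline Date". That is normally Visit 2; the Visit 1a value serves only if no later one exists.

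Two scores are planned before treatment. Section 7.1.1 says of the questionnaire: "It is administered at screening, baseline, and at each of the scheduled post-baseline treatment phase visits". The schedule in Appendix 2 marks IPSS at Visit 1a and Visit 2 and leaves Visit 1b blank. Item 07 in Section 4.1.3 ties eligibility to a screening IPSS of at least 12, so Visit 1a is where that score arises. Table 2.2 in Appendix 15 tabulates the Visit 1a score. No model names it, and it is not among the Appendix 10 covariates.

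**The concern.** IPSS is self-reported and varies from day to day, so one reading measures a man's underlying severity with error. A second reading taken before randomization will usually predict the Month 24 score somewhat better alongside the first than the first does alone. It cannot be affected by treatment, so including it leaves the target of the linear-model comparison unchanged and cannot raise its large-sample variance.

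What is at stake is the width of the confidence interval and the power of the Month 24 test. Under Appendix 11 that test is the gate to formal significance for the secondary endpoints and the earlier time points. Section 9 repeats every analysis within each country, drops cluster from those models and concedes that they are underpowered. One baseline score is then the only covariate left.

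**Working it through.** **Inputs from the SAP.** Two-sided 0.05 test; baseline-adjusted linear model; IPSS at Visits 1a and 2; entry cut of 12 on the screening score. The SAP states no sample size, power, SD or between-visit correlation, so there is no figure of the plan's own to reproduce.

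**Assumed inputs.** Before the entry cut, screening IPSS is normal with mean 16 and SD 6.5, limited to 12–35 by the cut and the top of the scale. Write *r12* for the Visit 1a–Visit 2 correlation, *r2y* for Visit 2–Month 24 and *r1y* for Visit 1a–Month 24, all before the cut.

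**Formulas.** Because baseline is a covariate, modelling the change or the Month 24 score gives the same residual variance. In units of the uncut variance:

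- Coefficient of Visit 1a: *b* = (*r1y* − *r12*·*r2y*)/(1 − *r12*²).
- Residual variance given both scores: *s*² = 1 − (*r1y*² + *r2y*² − 2·*r1y*·*r2y*·*r12*)/(1 − *r12*²).
- The cut shrinks the Visit 1a variance by a factor *k*. For a normal cut at (12 − 16)/6.5 = −0.615 and (35 − 16)/6.5 = 2.923, *k* = 0.501.
- Visit 1a variance left after Visit 2: *V* = *k*(1 − *r12*²)/(*k*·*r12*² + 1 − *r12*²).
- Fall in residual variance: *b*²*V*/(*b*²*V* + *s*²).
- New power from nominal 80%: Φ((1.960 + 0.842)/√(1 − fall) − 1.960).

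**Worked case, 0.6/0.5/0.5.** *b* = (0.5 − 0.30)/0.64 = 0.3125. *s*² = 1 − (0.25 + 0.25 − 0.30)/0.64 = 0.6875. *V* = 0.501 × 0.64/(0.501 × 0.36 + 0.64) = 0.391. The fall is 0.0977 × 0.391/(0.0382 + 0.6875) = 5.3%. Power is Φ(2.802/0.973 − 1.960) = 82.1%.

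| r12 / r2y / r1y | Fall, no cut | Fall, with cut | 80% power becomes |
|---|---|---|---|
| 0.7 / 0.5 / 0.35 | 0% | 0% | 80.0% |
| 0.7 / 0.5 / 0.40 | 0.65% | 0.4% | 80.2% |
| 0.8 / 0.5 / 0.45 | 0.9% | 0.7% | 80.3% |
| 0.6 / 0.5 / 0.45 | 4.7% | 2.9% | 81.1% |
| 0.7 / 0.5 / 0.50 | 5.9% | 4.0% | 81.6% |
| 0.6 / 0.5 / 0.50 | 8.3% | 5.3% | 82.1% |
| 0.7 / 0.6 / 0.60 | 9.9% | 6.8% | 82.7% |

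In the first row *r1y* = *r12*·*r2y*, so Visit 1a adds nothing once Visit 2 is known. A 7% fall in variance is a 3.6% fall in the standard error.

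**Larger values.** If all three correlations are equal at 0.5 to 0.6, simulation with the cut and an assumed mean of 14 or 18 gives 6.3% to 10.7%. That requires scores about six weeks apart (14 days plus 28 days in Appendix 2) to correlate no better than scores two years apart. I do not rest the size on it.

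**Qmax.** Section 8.1.4 states that "Qmax and associated total voided volume are measured at screening (Visit 1a with possible repeat at Visit 1b), baseline", so a second value exists there too. Item 10 in Section 4.1.3 restricts the screening value on both sides, above 5 and up to 15 mL/sec. With all correlations 0.5 the untruncated fall is 11.1%. With that window and an assumed mean of 10–12 and SD of 4–5, *k* is 0.28 to 0.42 and the same formula gives 4.1% to 5.8%, about half.

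**The case against.** The strongest reply is that nothing here is wrong. Treatment, cluster and baseline form a standard covariance analysis, stated consistently in Sections 1 and 7.1.2 and in Appendix 10, and any plan could be asked for one more covariate. That stands to this extent: a reader might infer that the primary test is flawed or biased, and the document does not support that. Omitting a prognostic covariate leaves the estimate unbiased and the error rate at its stated level.

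It is also fair that the gain may be nil. Visit 1a precedes a four-week placebo run-in, is selected at 12 or more, and lies further from Month 24 than Visit 2 does. All three weaken what it adds. A reader might infer that precision is certainly being lost; without a correlation in the SAP this cannot be claimed.

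Nor is the Visit 1a score wholly unused. It serves eligibility, is tabulated, and becomes the baseline if Visit 2 is missing. Appendix 10 sets its covariate list as a minimum, which leaves room for a supportive Visit 1a term.

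Last, Section 2.1 declares no departure from the protocol-defined analysis, and Appendix 4 shows that randomization is over. Changing a primary model at that stage, for submissions in four countries, is a real though small cost. It does not defeat the point, provided the change is fixed before unblinding and recorded.

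**Conclusion.** The point holds as an optional efficiency improvement, not as an error. Both models use one of two pre-treatment IPSS scores. Adding the other would cut the residual variance of the Month 24 comparison by 0% to about 7%, taking a nominal 80% power to about 80–83%. This rests on assumed correlations (0.6–0.8 between the two pre-treatment scores, 0.35–0.6 with Month 24), an assumed screening distribution and the entry cut of 12.

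The same covariate could be added for BII and BHS (Visits 1a and 2), PAS SFI (Visits 1b and 2) and Qmax. A reader might carry an untruncated figure of around 11% over to Qmax; the two-sided screening window rules that out.

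**What to change.** Before unblinding:

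- In Section 7.1.2 and Appendix 10, add the Visit 1a IPSS total as a second continuous covariate in the Month 24 model: treatment, cluster, baseline IPSS, Visit 1a IPSS.
- In Appendix 13, add Visit 1a IPSS and its interaction with visit.
- Keep change from the Appendix 6 baseline as the endpoint.
- Set a missing Visit 1a score, or one that already serves as baseline, to the pooled mean across both arms, so that nobody is dropped or counted twice.
- Record the departure from the protocol-defined model in Section 2.1.

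The same may be done for BII, BHS, PAS SFI and Qmax; for Qmax use only screening values that meet the 125 ml voided-volume rule in Section 8.1.4. If the sponsor prefers to leave the primary model as it is, prespecifying the two-score model as a supportive analysis is the least useful step worth taking.

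The cost is one degree of freedom (one per visit in the MMRM), a short text change for each model, the rule for missing values and the documented departure. No new data are needed.

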11.11. Appendix 11: Multiple Comparisons and Multiplicity

Results of all planned statistical analyses and thus all planned p-values will be reported. P-values ≤ 0.05 will be considered formally statistically significant if the below described conditions are satisfied for multiple endpoints and multiple time points. Otherwise p-values ≤ 0.05 will be considered nominally significant.

The comparisons are in terms of two treatment arms, Combination and Tamsulosin, so no multiplicity adjustment for treatment is necessary.

Multiplicity adjustment for multiple endpoints is described in this paragraph. For the primary efficacy endpoint, IPSS change from baseline at Month 24, if the Month 24 two-sided p-value is ≤ 0.05 and the treatment difference supports Combination superiority versus Tamsulosin, then formal statistical significance is declared and testing of each secondary endpoint may occur. For secondary endpoints evaluated at multiple time points, then the testing will begin at Month 24. For purposes of statistical testing, there is no hierarchical order assigned to the set of secondary endpoints at Month 24.

Multiplicity adjustment for multiple time points is described in this paragraph. For any endpoint that is tested over different visits, a step-down procedure for interpreting the p-values will be adopted. The final time point (Month 24) will be tested first. If the Month 24 two-sided p-value is ≤ 0.05 and the treatment difference supports Combination superiority versus Tamsulosin, the time point immediately preceding it will be interpreted for formal statistical significance; otherwise formal interpretation of significance will stop, but interpretation of nominal significance will continue for preceding endpoints. The interpretation of formal statistical significance will continue this way in a stepwise manner through all time points.

As an example, the time point testing visit sequence for the primary efficacy endpoint is: Month 24, Month 21, Month 18, Month 15, Month 12, Month 9, Month 6, and (last) Month 3.

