2.4. Statistical Hypotheses

The primary endpoint is change from baseline IPSS. Let the following represent the mean change from baseline IPSS for each treatment group:

$H_{dut+tam}$: Combination (dutasteride 0.5mg and tamsulosin 0.2mg) treatment group

H_{tam} : Tamsulosin 0.2mg treatment group

Then the primary null and alternative hypotheses to be tested at Year 2 are as follows:

Description	Null Hypothesis	Alternative Hypothesis
Combination versus tamsulosin 0.2mg	$H_{dut+tam} = H_{tam}$	$H_{dut+tam} \neq H_{tam}$

Two-sided tests of the null hypothesis will be conducted at the 0.05 level of significance to show superiority of the combination treatment group compared to tamsulosin 0.2mg at 2 years of treatment.

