8.1.2. IPSS Improvement Levels

Symptom improvement is assessed using IPSS continuous data changes as the primary efficacy endpoint and using categorical changes as a secondary efficacy endpoint. Improvement is a post-baseline score which is lower than the baseline score. Worsening is a post-baseline score which is higher than the baseline score. The number and percentage of subjects with IPSS percentage change from baseline categories of 1) improvement, 2) no change, and 3) worsening will be summarized by treatment group using both the LOCF and At Visit approaches at each scheduled post-baseline assessment.

IPSS change from baseline will be presented using five improvement levels: ≥ 1 point through ≥ 5 points. IPSS percentage change from baseline will be presented using seven improvement levels: $>0\%$, $\geq 10\%$, $\geq 20\%$, $\geq 25\%$, $\geq 30\%$, $\geq 40\%$, and $\geq 50\%$. Treatment comparisons for combination versus tamsulosin will be performed for each ≥ 2 points, ≥ 3 points, and $\geq 25\%$ using a Mantel-Haenszel test controlling for cluster at alpha=0.05.

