The primary analysis of this endpoint will compare combination treatment versus tamsulosin treatment in terms of time to first AUR or BPH-related surgery for the ITT population using a log rank test stratified by cluster at the 0.05 level of significance. The relative risk (hazard ratio) for the treatment effect and associated two-sided 95% confidence intervals will be estimated using a Cox proportional hazards model with treatment as the only covariate and stratified by cluster. Estimates and corresponding confidence intervals for the relative risk (hazard ratio) and risk reduction (1-hazard ratio) of combination treatment versus tamsulosin treatment will be presented along with the log rank p-value. Assessment of the Cox modeling procedure will include examination of diagnostic plots to assess the assumption of proportional hazards and the review of results obtained by fitting separate models by cluster to assess the homogeneity of treatment effect across clusters.

Time to first AUR or BPH-related surgery, expressed as months, will be summarized by treatment group for the ITT population using product-limit estimates computed by the Kaplan-Meier method and displayed graphically as Kaplan-Meier curves.

The number of subjects with at least one AUR or BPH-related surgery will be summarized by treatment group across the 2 year period. The crude rate of AUR or BPH-related surgery incidence will be calculated using the Intent-to-Treat population of each treatment as the denominator; the associated 95% confidence interval will be output. This crude rate will be compared for combination treatment versus tamsulosin treatment using the Mantel-Haenszel test stratified by cluster at the 0.05 level of significance.

AUR or BPH-related surgery event details per subject will be summarized by treatment and will include: event component (first occurring of either AUR or BPH-related surgery) and time period of first occurring event (during treatment or after treatment stop). BPH-relatedness (yes/no) and AUR precipitating factors will be summarized by treatment for subjects in which AUR is the primary efficacy event's initial component. Types of surgery/intervention will be summarized by treatment for subjects in which BPH-related surgery is the primary efficacy event's initial component.

Time from last dose to first AUR or BPH-related surgery event will be summarized for those subjects experiencing the first event after treatment stop.

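### Once the primary endpoint passes, Appendix 11 calls each secondary p-value of 0.05 or less formally significant, with no error control across the 13 secondary efficacy and health-outcome endpoints

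*SAP*

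**What the plan says.** Section 2.4 sets one formal hypothesis, IPSS change at Year 2, tested two-sided at 0.05. Appendix 11 (Section 11.11) governs everything beyond it and defines two labels. A p-value of 0.05 or less "will be considered formally statistically significant if the below described conditions are satisfied for multiple endpoints and multiple time points"; otherwise it is only nominally significant.

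The paragraph on multiple endpoints contains one condition. If the primary p-value is 0.05 or less in favour of combination, "then formal statistical significance is declared and testing of each secondary endpoint may occur". It then adds: "For purposes of statistical testing, there is no hierarchical order assigned to the set of secondary endpoints at Month 24".

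The paragraph on multiple time points works inside a single endpoint: "For any endpoint that is tested over different visits, a step-down procedure for interpreting the p-values will be adopted".

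The sections on individual endpoints each set the full 0.05. Examples are the IPSS responder comparisons in Section 8.1.2 ("using a Mantel-Haenszel test controlling for cluster at alpha=0.05") and the crude event rate in Section 8.1.5 ("using the Mantel-Haenszel test stratified by cluster at the 0.05 level of significance"). Section 8.3 places the health outcomes under Appendix 11 as well.

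**The concern.** Appendix 11 announces an adjustment for multiple endpoints, but across the secondary endpoints it supplies none. No alpha split, Bonferroni, Holm, Hochberg or fixed sequence across them appears anywhere in the SAP. After a primary success every secondary endpoint is tested in parallel at 0.05.

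Leaving secondary endpoints unadjusted can be defended when their p-values are presented as nominal or supportive. This plan has a nominal label and withholds it from these results. A reader will take *formally significant* to mean that the error rate over the claims made is controlled, and the rule does not provide that. Sections 3.2 and 9 say the analyses support regulatory submissions, with one anticipated in each of four countries, so the label is likely to carry weight.

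**Working it through.** **The plan's own figure.** The SAP states no family-wise error rate for the secondary endpoints, so there is nothing to reproduce beyond the primary test's two-sided 0.05, which is a single test at that level.

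**Count** (Section 2.2; tests in Sections 8.1.2–8.1.5 and 8.3.1–8.3.3; LOCF is primary, so At Visit repeats are not counted):

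| Group | Endpoints | Tests |
|---|---|---|
| Prostate volume, % change | 1 | 1 |
| IPSS improvement: 2 points, 3 points, 25% | 3 | 3 |
| Qmax change | 1 | 1 |
| Qmax improvement: 3 mL/sec, 30% | 2 | 2 |
| AUR or surgery; AUR; surgery | 3 | 6 (log-rank and Mantel-Haenszel each) |
| BHS, BII, PAS-SFI | 3 | 3 |
| **Total** | **13** | **16** |

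The 25% prostate volume improvement test in Section 8.1.3 would be a 17th test, but Section 2.2 does not list it as an endpoint. Earlier IPSS visits are also classed as secondary, but the step-down orders them.

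**Formulas.** With the gate open and k true null endpoints, each tested at 0.05, independence gives

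- any false formal result: 1 − 0.95^k
- a false result favouring combination: 1 − 0.975^k, against a target of 0.025

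Positive correlation lowers both, so independence is an upper bound. For correlated tests I simulated equicorrelated normal statistics. The correlations are assumptions; the SAP gives none.

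| Null endpoints | Correlation | Any false formal result | Favouring combination |
|---|---|---|---|
| 4 (three event endpoints, PAS-SFI) | 0.7 | 0.130 | 0.065 |
| | 0.5 | 0.156 | 0.078 |
| | 0.3 | 0.174 | 0.087 |
| | 0 | 1 − 0.95^4 = 0.185 | 1 − 0.975^4 = 0.096 |
| 13 (all) | 0.7 | 0.241 | 0.121 |
| | 0.5 | 0.335 | 0.167 |
| | 0.3 | 0.418 | 0.213 |
| | 0 | 1 − 0.95^13 = 0.487 | 1 − 0.975^13 = 0.280 |

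**Why endpoints and not tests.** The log-rank and crude-rate tests of one event use the same events. Under illustrative assumptions that are not in the SAP (300 per arm, unstratified tests, AUR 4–8%, surgery 3–5%, 20% early censoring, PAS-SFI independent), their correlation was about 0.997. At least one p-value of 0.05 or less among the six event tests and PAS-SFI occurred in 15–17% of simulated trials (about 8% in one direction). Dropping the crude-rate tests moved the two-sided figure only from 0.165 to 0.159.

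**If the primary null is true.** The gate opens falsely in favour of combination with probability 0.025, which caps any false secondary claim. With 16 secondary tests and correlations of 0 to 0.5 with the primary, the simulated rate was 0.014–0.024.

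**The case against.** The strongest defence has four parts.

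- **The rule is disclosed in advance.** Appendix 11 says openly that there is no order and that all planned p-values will be reported, so a reader can apply any correction. This stands as far as transparency goes. It does not supply the control that the formal label implies.
- **Some control exists.** The directional gate holds false secondary claims to 2.5% or less when the primary null is true, and the step-down handles visits within an endpoint. This stands. A reader might infer that the secondary endpoints have no error control at all; the text does not support that. The gap is across endpoints, after a primary success.
- **The worst-case number is not realistic.** Counting 16 independent null tests gives 1 − 0.95^16 = 56%, and a reader might take that as the size of the problem. It counts each event endpoint twice and ignores the overlap between the composite and its components and between nested cut-offs. It also sits badly with an open gate: three of the 16 tests are cut-offs of the IPSS change itself and would hardly all be null when mean IPSS change truly differs. This stands, and 56% should not be used as the estimate.
- **The primary conclusion is untouched.** Its alpha and test do not change, and the relabelling option alters no estimate, interval or p-value. This also stands, and limits the severity.

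**Conclusion.** The point holds in a limited form. After a primary success, 13 secondary efficacy and health-outcome endpoints are each tested at an unadjusted 0.05 and each can be declared formally significant, with no control across them.

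If the null endpoints are the three event endpoints and PAS-SFI, the chance of at least one false formal result is about 13–17%, or 7–9% in favour of combination. If all 13 are null it is about 24–42% (12–21%), with 49% (28%) as the bound under independence. All of these exceed the 5% and 2.5% that the label suggests. The figures rest on assumed equal correlations of 0.3 to 0.7 and on assumptions about which endpoints are null. The SAP supplies neither.

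This should be fixed, but it is a fault in the secondary claims only. The documents do not support reading it as a weakness of the primary analysis.

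**What to change.** Amend Appendix 11 before unblinding, in one of two ways.

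1. **Relabel.** State that only the primary endpoint and its visit step-down can be formally significant, and that every other secondary p-value is nominal. This uses the plan's own vocabulary and costs the primary no power.
2. **Control.** Apply Holm (valid under any correlation) or Hochberg (which relies on suitable positive dependence) at 0.05 over the Month 24 secondary endpoints. The smallest p-value under Holm would face 0.05/13 = 0.0038. Use one test per event endpoint: the log-rank, which Section 8.1.5 already names as the primary analysis, with the crude-rate comparison descriptive. Let each endpoint's visit step-down be formal only after its adjusted Month 24 rejection, and run it at that endpoint's adjusted level.

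Under the second option, list the family explicitly. Section 2.2 also places PSA and post-void residual volume under secondary endpoints, both have planned comparisons (Sections 8.2.7 and 8.2.8), and Appendix 11 does not say whether they belong.

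The cost is that some secondary results with p-values between the adjusted level and 0.05 lose the formal label; under relabelling, all of them do. Section 2.1 now reports no change from the protocol's planned analysis. If the protocol states the same rule, Section 2.1 must record the departure.
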